4.5.2. Immunogenicity

Endpoint titres (concentration) of systemic CN54rgp140-specific IgG antibodies at 4 weeks from the final vaccinations will be described (mean and 95% C.I. – log10 scale - or median and IQR – original scale) by group for the responders, and compared using the Wilcoxon rank-sum test.

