7. ASSESSMENTS AND FOLLOW-UP

7.1 Duration of Follow-up and Schedule

The assessments that will be performed at each visit are described in **Table 5**.

Participants will be required to make a minimum of 11 scheduled outpatient visits over the course of up to 30 weeks. Time 0 will start on the day of enrolment, which is also the day of randomisation and first immunisation.

Screening can take place up to 6 weeks (42 days) before time 0.

Immunisations will take place at weeks 0, 4, 8 and 20.

A 12th scheduled outpatient visit, at Week 44, will only take place for participants known to have responded to the vaccine.

Serum will be collected for immunogenicity at enrolment, and weeks 4, 5, 8, 9, 20, 21, 22 (the primary endpoint), 24 and 44. Peripheral blood mononuclear cells (PBMC) will be collected at enrolment, and weeks 4, 8, 20, 21, 22, 24 and 44.

Adverse events will be assessed during the enrolment visit before and after immunisation and at every visit thereafter up to (and including) Week 22. Routine laboratory safety parameters will be collected at screening, enrolment, and weeks 1, 4, 5, 8, 9, 20, 21 and 22, and at any other visit if clinically indicated.

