9. WITHDRAWAL OF PARTICIPANTS

Withdrawal from the trial means stopping all further visits.

The reason(s) for withdrawal should be recorded on the Status CRF.

All participants are free to withdraw from the trial at any time, for any reason, without affecting their future medical care. An investigator may decide to withdraw a participant if the investigator deems that continuing might compromise participant wellbeing or interfere with the achievement of the trial's objectives.

Participants who are withdrawn due to an adverse event (AE) will be followed-up until the event has stabilised.

Withdrawn participants who have received any immunisations should be asked to undergo the procedures scheduled for the primary endpoint visit (Visit 10, week 22).

Policy for replacing withdrawals

Additional volunteers will be enrolled to replace early withdrawals or those who have discontinued their immunisations early, with the aim of having 24 subjects complete the study with no major protocol deviations. However, no more than 30 individuals in total will be exposed to the vaccine.

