10.2.1.2 Immunogenicity

- The magnitude of antigen specific systemic IgG antibody binding responses (µg/ml) 2 weeks after the final vaccination.

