10.4.2 Immunogenicity

10.4.2.1 Primary Immunogenicity Outcomes

All serum samples will be screened for antigen specific antibodies IgG (and IgA). The absolute levels of antibody in samples that are found to be positive will be determined using a standardised and quantitative ELISA developed in [name]'s laboratory at Imperial College London. In this sandwich capture ELISA, the Ab of interest is captured by the relevant target antigen and then detected using a labelled isotype specific secondary Ab. An estimate of the concentration of Ab in the sample is calculated by interpolation relative to a standard curve based on titration of purified human standards IgG or IgA captured by anti-human kappa/lambda-specific antibodies. The number of 'responders' in each assay will be presented by time-point and group as a proportion with 95% confidence interval. A 'responder' will be defined as a participant in whom a response was detected in at least one post treatment immunogenicity sample. Titres of antigen specific antibodies will be described by time-point and group, and compared using rank tests where appropriate. Although all samples will be processed, the analyses will be for the per-protocol population and conducted in [name]'s laboratory.

10.4.3

Exploratory Immunogenicity Outcomes

The proportion of individuals mounting a B cell response using frozen PBMC will be determined by B cell Elispot assay for antigen induced IgG production from antibody secreting cells (ASC's). CN54gp140 specific responses will be analysed as well as total IgG and compared between vaccine groups.

In addition vaccine induced T cell responses will be analysed by T cell Elispot assay for IFN- γ production on frozen PBMC samples and the proportion of individuals mounting a response quantified as SFU (spot forming units) compared between vaccine groups. These exploratory analyses will use descriptive statistics and will be conducted in [name]'s laboratory.

10.4.4

Safety Outcomes

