CUTHIVAC 002

Statistical Analysis Plan

Version: **v1.0**

Date: **10/10/2017**

Authors:

Name: **[name]**

Signature:

Approvals:

Name:

Signature:

Revision History:

Version	Author	Date	Reason for Revision

Contents

1.	Trial overview.....	3
1.1.	Primary Objectives.....	3
1.2.	Secondary Objectives.....	4
1.3.	Exploratory Objectives.....	4
2.	General Considerations.....	4
2.1.	Randomisation	4
2.2.	Sample Size	4
2.3.	Analysis datasets.....	4
2.4.	Missing Data.....	4
3.	Endpoint Definitions	5
3.1.	Primary Endpoints.....	5
3.1.1.	Safety	5
3.1.2.	Immunogenicity	5
3.2.	Secondary Endpoint.....	6
3.2.1.	Safety	6
3.3.	Exploratory Endpoints.....	6
3.3.1.	Immunogenicity	6
3.3.2.	Tolerability	6
4.	Statistical Analyses.....	6
4.1.	Enrolment Description	7
4.2.	Baseline Characteristics	7
4.3.	Follow-up Description.....	8
4.4.	Interim Analysis.....	8
4.5.	Primary Analysis.....	8
4.5.1.	Safety	8
4.5.2.	Immunogenicity	8
4.6.	Secondary Analysis.....	8
4.6.1.	Safety	8
4.7.	Exploratory Analysis.....	9
4.8.	Subgroup Analysis.....	9
A.	Tables	10

1. Trial overview

CUTHIVAC002 is an open-label randomised phase I study aimed at exploring the safety and immunogenicity of two different modes of delivery of a deoxyribonucleic acid (DNA) vaccine (DNA-C CN54ENV) via combined intramuscular (IM) and intradermal (ID) methods with and without electroporation (EP), and boosted with recombinant HIV CN54gp140 administered by intradermal injection in healthy volunteers. The aim of this study is to identify optimal DNA delivery conditions for promoting enhanced antibody responses to boosting with recombinant protein by the intradermal method.

Participants are randomised 1:1:1 to ID/EP, IM/EP or ID/IM/EP, the randomisation is unblinded. Following the immunisation schedule of table 1, participants return at weeks 4, 8 and 20. Primary immunogenicity assessment is at week 22.

Table 1: Immunisation schedules

Group	Immunization: Dose of DNA			Immunization: Dose of CN54gp140
	Dose 1 at WK 0	Dose 2 at WK 4	Dose 3 at WK 8	Dose 4 at WK 20
1 N=8	0.6mg ID*/ EP 2mg IM**	0.6mg ID*/ EP 2mg IM**	0.6mg ID*/ EP 2mg IM**	50ug ID***
2 N=8	0.6mg ID* 2mg IM**/ EP	0.6mg ID* 2mg IM**/ EP	0.6mg ID* 2mg IM**/ EP	50ug ID***
3 N=8	0.6mg ID*/ EP 2mg IM**/ EP	0.6mg ID*/ EP 2mg IM**/ EP	0.6mg ID*/ EP 2mg IM**/ EP	50ug ID***

* 1 x 0.15ml injections ID via needle – into upper arm with/without electroporation (EP)

** 1 x 0.5ml injections IM – into the upper thigh with/without electroporation (EP)

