3.1.2. Immunogenicity

The primary immunogenicity endpoint is the titre of systemic CN54rgp140-specific IgG antibodies measured 2 weeks \pm 3-day window after a participant's scheduled final vaccination (any exception to the 3-day window to be discussed by the TMG). Responses are measured using a semi-quantitative sandwich ELISA assay and defined as positive when exceeding mean OD at 450nm plus 3 SDs at a 1/100 dilution for a panel of serum samples obtained from 20 HIV negative volunteers. Samples deemed "response positive" are analysed further in a titration assay where samples are subsequently diluted to achieve at

least two OD at 450nm values that fall on the linear part of the relevant human IgG or IgA standard curve of known concentration. These values are interpolated automatically by the ELISA software (SoftMax Pro v 5.4) to give two extrapolated values in $\mu\text{g/ml}$. The mean of these 2 values is then reported as the “titre” of antigen specific IgG or IgA for response detected samples.

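### The SAP's primary IgG analysis is set 4 weeks after the final vaccination (week 24), but the primary endpoint is defined at 2 weeks (week 22)

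*SAP*

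**What the plan says.** SAP 4.5.2 sits under the heading Primary Analysis and gives the whole analysis of the primary immunogenicity endpoint: "Endpoint titres (concentration) of systemic CN54rgp140-specific IgG antibodies at 4 weeks from the final vaccinations will be described" by group among responders, then compared with a Wilcoxon rank-sum test.

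SAP 3.1.2 defines that endpoint differently: "The primary immunogenicity endpoint is the titre of systemic CN54rgp140-specific IgG antibodies measured 2 weeks" after the scheduled final vaccination, with a 3-day window either side and "any exception to the 3-day window to be discussed by the TMG". SAP 1 says: "Primary immunogenicity assessment is at week 22".

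The protocol agrees with SAP 3.1.2. Sections 1.1.6 and 10.2.1.2 place the IgG magnitude "2 weeks after the final vaccination". Section 7.1 lists serum collection after enrolment at "weeks 4, 5, 8, 9, 20, 21, 22 (the primary endpoint), 24 and 44". Section 9 calls week 22 (visit 10) the primary endpoint visit and asks withdrawn participants who were immunised to undergo its procedures.

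Protocol 10.4.2.1 outlines the analysis without choosing a time point: "Titres of antigen specific antibodies will be described by time-point and group, and compared using rank tests where appropriate".

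**The concern.** One primary endpoint has two stated time points, and the one that differs is in the section an analyst would follow. Week 24 is a real visit (visit 11) with its own serum sample, so 4.5.2 can be carried out exactly as written and would yield a primary result from a sample that does not meet the endpoint definition. Either the week-22 or the week-24 result could be called primary while citing the SAP. Prespecification is meant to remove that choice.

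Two features of the plan make this more than cosmetic.

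- SAP 4.5.1 (safety) refers back to its definition in 3.1.1. SAP 4.5.2 has no such reference to 3.1.2; it states its own time point and so does not inherit the right one.
- SAP 4 says the immunogenicity data are not held at the trials unit and will be analysed elsewhere, so another group has to work from the written text.

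The conflict also leaves unclear which visit is meant when SAP 2.4 promises to describe missing data on the primary immunogenicity outcome.

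**Working it through.** **Inputs**

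- Final (fourth) vaccination: week 20 (protocol 6.1 and Table 1; SAP Table 1).
- Time after it in the endpoint definition: 2 weeks (SAP 3.1.2; protocol 1.1.6 and 10.2.1.2).
- Time after it in the primary analysis: 4 weeks (SAP 4.5.2).
- Window for the week-22 and week-24 visits: ±3 days, counted from the fourth vaccination (protocol 7.1.2). SAP 3.1.2 also uses ±3 days for the endpoint.
- Week-22 visit-compliance window in SAP 4.3: ±7 days.

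**Step 1: reproduce the stated endpoint week.** Study week = week of final vaccination + weeks after it = 20 + 2 = 22. This matches SAP 1 and protocol 7.1 and 9.

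**Step 2: apply the same formula to SAP 4.5.2.** 20 + 4 = 24. The difference is 24 − 22 = 2 weeks, or 14 days.

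**Step 3: could one sample satisfy both?** In days after the fourth vaccination:

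- Week 22: 14 ± 3 = days 11–17.
- Week 24: 28 ± 3 = days 25–31.
- Days 18–24, 7 days in all, lie between the two windows.

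The windows do not overlap. Even the wider SAP 4.3 window for week 22, 14 ± 7 = days 7–21, stops short of day 25.

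**Step 4: set the statements side by side.**

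| Place | Primary IgG time point |
|---|---|
| Protocol 1.1.6 | 2 weeks |
| Protocol 7.1 | week 22 |
| Protocol 9 | week 22 |
| Protocol 10.2.1.2 | 2 weeks |
| SAP 1 | week 22 |
| SAP 3.1.2 | 2 weeks ±3 days |
| SAP 4.5.2 | 4 weeks (week 24) |

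Six statements give 2 weeks or week 22; one gives 4 weeks. Elsewhere, an endpoint four weeks after the final immunisation appears only for the exploratory mucosal antibodies (protocol 1.1.6 and 10.2.3; SAP 3.3.1), which is a different measure.

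**Step 5: the related window in SAP 4.3.** Its ±7 days covers days 7–21, which is 15 days. The endpoint window, days 11–17, is 7 days. So 15 − 7 = 8 days (7–10 and 18–21) count as visit-compliant in SAP 4.3 but fall outside the endpoint window in SAP 3.1.2. This concerns visit compliance only and does not override 3.1.2.

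**The case against.** The strongest reply is that the intended time point is not really in doubt. SAP 3.1.2 is headed as the endpoint definition, SAP 4.5.2 does not announce a new endpoint, and the count is six to one, so 4.5.2 is most likely a drafting slip. That is a fair inference, although no document says so. It tells us which way to correct 4.5.2, but it does not make the section right as written.

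A second reply is that week-22 titres would be reported anyway, because protocol 10.4.2.1 asks for results by time point and group and protocol 10.4 says the SAP is to be based on that summary. This stands, and it limits the harm: the risk is to which result is labelled primary, not to whether week 22 appears. It does not settle the conflict, because 10.4.2.1 names no primary time point.

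Third, the immunology is intended as mainly descriptive and the trial is not powered for group comparisons (protocol 2.2.1 and 10.3; SAP 2.2). Laboratory staff are blind to regimen (protocol 2.2.5 and 5.2). No sample size or error rate depends on this time point. All of that stands, and neither power loss nor assay bias is claimed. A descriptive trial still needs one identified sample for its primary description, and 4.5.2 attaches a test to it.

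Fourth, the immunogenicity analysis is done in the laboratory and the SAP's table shells contain no immunogenicity table, so how far 4.5.2 governs the actual work is uncertain. This cuts both ways: it may weaken the practical force of the error, but it also leaves the laboratory without an unambiguous SAP instruction.

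Finally, week 22 is also the final safety visit, so the request to withdrawn participants in protocol 9 is not evidence about immunogenicity alone. That is correct; the section counts here only because it names week 22 as the primary endpoint visit.

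**Conclusion.** The concern holds. SAP 4.5.2 assigns the primary immunogenicity analysis to week 24, which is not the primary endpoint visit in any other part of the SAP or protocol. The discrepancy is 14 days, between two scheduled serum samples whose ±3-day windows do not overlap. It should be corrected because it concerns the trial's only primary immunogenicity endpoint.

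The day counts assume that both windows are measured from the date of the fourth vaccination, as protocol 7.1.2 states. Measuring both from the scheduled date instead would leave the 14-day separation unchanged. The documents give nothing from which to estimate how titres differ between weeks 22 and 24, so no size of effect on the result is stated.

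The ±7-day week-22 window in SAP 4.3 is a smaller, separate mismatch with protocol 7.1.2 and SAP 3.1.2, and the conclusion does not depend on it.

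**What to change.** In SAP 4.5.2, replace the 4-week time point with: *at week 22, two weeks (±3 days) after the fourth vaccination, as defined in 3.1.2*. The added cross-reference makes the immunogenicity section work as the safety section 4.5.1 does. If week-24 titres are wanted, list them as a further time point that is not primary. Settle this before the immunogenicity analysis is run.

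In the same edit, align the week-22 compliance window in SAP 4.3 with the ±3 days in SAP 3.1.2 and protocol 7.1.2. The rest of that paragraph should be checked against protocol 7.1.2 at the same time: it gives weeks 1, 5 and 9 as ±3 days where the protocol has −3 to +7, and it gives no window for the week-20 or week-24 visits.

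The cost is SAP wording only. No new samples, visits or data are needed, because serum is already scheduled at both weeks.

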All volunteers will receive 3 immunisations of 2.0mg DNA IM and 0.6mg DNA ID and the immunisations will be administered with or without EP as described in table 1. In a supportive rabbit GLP toxicity study which was carried out with the same vaccine, the individual IM dose was 2mg, this was given for up to six administrations was shown to be well tolerated in rabbits (CR 525569) and lack of DNA persistence or distribution beyond the site of administration was demonstrated in rats (CR525574). Furthermore, a previous Phase I trial to use electroporation (EP) for the delivery of a DNA vaccine for HIV demonstrated increased immunogenicity in the absence of associated safety concerns [44] [62].

CN54gp140 Doses

We will give 1 immunisation of 50 μ g CN54gp140. In MucoVac 2 there was no significant impact on the magnitude of the responses after reducing the dose from 100 μ g to 20 μ g although this was in the presence of adjuvant.

2.2.4

Possible Next Steps

The following hypotheses will be explored with a view to informing the design of future trials both in terms of size and selection of methods:

- That each of the methods and combination regimens delivered with and without EP will be safe and acceptable
 - If any of the methods or regimens have unacceptable safety defined in terms of the proportion of participants that experience a grade 3 or above solicited adverse event or an event that leads to an investigator decision to discontinue immunisations, then there will be no further exploration of the route with the product/regimen.
- That immunisation via the combined IM+ID methods will elicit balanced immune responses.
- That EP will augment antibody responses to both ID and IM.

- That the greatest proportion of individuals will respond and make significantly greater antibody responses in group 3 (ID/EP + IM/EP) relative to the other groups. If EP is shown to impact upon the proportion of individuals making systemic IgG without compromising safety/tolerability, the strategy would be taken forward into future trials.

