3.3.2. Tolerability

- Pain scores at 0, 10 and 30 minutes following vaccination with EP

4. Statistical Analyses

Analyses of safety and tolerability endpoints for randomized participants will be performed at the MRC CTU at UCL. Immunogenicity data are not held at the CTU, and will be analysed elsewhere.

Adverse events and vaccine responses will be described as frequencies with 95% confidence intervals. Confidence intervals will be calculated using Wilson intervals, suitable for small sample sizes (table 3).

Table 3. Wilson intervals

Number of events	N=8		N=7		N=6		N=5	
	%	95% CI						
0	0%	0,32%	0%	0,35%	0%	0,39%	0%	0,43%
1	13%	2,47%	14%	3,51%	17%	3,56%	20%	4,62%
2	25%	7,59%	29%	8,64%	33%	10,70%	40%	12,77%
3	38%	14,69%	43%	16,75%	50%	19,81%	60%	23,88%
4	50%	22,78%	57%	25,84%	67%	30,90%	80%	38,96%
5	63%	31,86%	71%	36,92%	83%	44,97%	100%	57,100%
6	75%	41,93%	86%	49,97%	100%	61,100%		
7	87%	53,98%	100%	65,100%				
8	100%	68,100%						

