4.7. Exploratory Analysis

Proportions and their 95% CIs will be reported for the categorical exploratory outcomes defined in 3.3, with arms compared using Fisher's exact test. For continuous outcomes means or medians will be presented as appropriate, and arms compared using Welch tests.

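### The primary IgG titre is summarised and tested among responders only, so the test does not compare the randomised groups and ignores differences in who responds

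*SAP*

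**What the plan says.** SAP 4.5.2 is the whole primary immunogenicity analysis. It describes endpoint titres "by group for the responders, and compared using the Wilcoxon rank-sum test". No other test is given for this endpoint.

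The related provisions are:

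- **Endpoint.** SAP 3.1.2: "The primary immunogenicity endpoint is the titre of systemic CN54rgp140-specific IgG antibodies measured 2 weeks" after the final vaccination, with a 3-day window. Protocol 10.2.1.2 also says 2 weeks, and protocol 7.1 names week 22. SAP 4.5.2 says 4 weeks.
- **Assay.** Protocol 10.4.2.1: "The absolute levels of antibody in samples that are found to be positive will be determined". SAP 3.1.2 likewise titrates only positive samples. A negative sample has no µg/ml value.
- **Responder.** Protocol 10.4.2.1: "defined as a participant in whom a response was detected in at least one post treatment immunogenicity sample".
- **Titre comparison in the protocol.** Section 10.4.2.1 allows rank tests where appropriate. It neither limits them to responders nor says how negatives enter.
- **Response proportion.** SAP section 4: "Adverse events and vaccine responses will be described as frequencies with 95% confidence intervals". Protocol 10.4.2.1 also gives the proportion by time-point and group with a 95% interval. Neither names a between-group test.
- **Fisher's exact test.** SAP 4.5.1 and 4.6.1 use it for safety. SAP 4.7 uses it for other outcomes: "Proportions and their 95% CIs will be reported for the categorical exploratory outcomes defined in 3.3". The list in 3.3 does not contain the primary serum IgG response.
- **Hypothesis and decision.** Protocol 2.2.4 expects "That the greatest proportion of individuals will respond and make significantly greater antibody responses in group 3". Its rule for taking the strategy forward begins: "If EP is shown to impact upon the proportion of individuals making systemic IgG without compromising safety/tolerability".

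**The concern.** Whether a participant responds is itself an effect of the allocated regimen. Once non-responders are removed, randomisation no longer protects the comparison. An arm that converts weak participants into low-titre responders can look no better, or even worse, than an arm in which those participants stayed negative and were dropped.

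Protocol 2.2.4 has two components, how many respond and how strongly. The test sees only the second, and only in a selected subset. The component it drops is the one the next-step rule depends on.

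Two further gaps sit in the same sentence. The time point conflicts with the endpoint definition. And if the protocol's any-sample definition of responder is used, a responder may be negative, with no titre, at the endpoint visit. The analysis cannot be programmed from this sentence without someone choosing.

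**Working it through.** **The plan's own figures.** The Wilson interval is [p + z²/2n ± z√(p(1−p)/n + z²/4n²)] / (1 + z²/n) with z = 1.96. For n = 8 it gives 7–59% for 2/8, 22–78% for 4/8 and 68–100% for 8/8, matching SAP Table 3. The documents state no power, titre SD, expected response rate or significance level for the titre test. Those used below are assumptions, with two-sided 0.05 throughout.

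**Constructed example, 8 per arm.** Arm A: 2/8 respond, at 2 and 4 µg/ml. Arm B: 8/8 respond, four at 2 and four at 4. Titres among responders have the same mix.

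- Responders only (2 v 8): arm A's rank sum is 3 + 8 = 11, exactly its null mean 2 × 11/2 = 11, so exact p = 1.00.
- All 16, negatives tied lowest: six negatives share rank 3.5, five values of 2 share rank 9, five values of 4 share rank 14. Arm A's rank sum is 6 × 3.5 + 9 + 14 = 44 against a null mean of 8 × 17/2 = 68. Of C(16,8) = 12,870 allocations, 70 are at least as extreme, so p = 70/12,870 = 0.0054.
- Fisher on 2/8 v 8/8: p = 0.0070.

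A milder case, 4/8 (1, 2, 4, 8) v 8/8 (1, 1, 2, 2, 4, 4, 8, 8), gives 1.00 among responders, 0.081 with everyone ranked and 0.077 by Fisher.

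**Smallest attainable p.** With a and b responders and no ties, the smallest exact two-sided p is 2/C(a+b, a). For 8 v 1 it is 2/9 = 0.22, for 6 v 2 it is 2/28 = 0.071, for 4 v 3 it is 2/35 = 0.057 and for 3 v 3 it is 2/20 = 0.10. In each case p<0.05 is impossible.

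**Attenuation.** Assume log10 titre is normal with equal SD, the better arm is shifted by 1 SD, and a sample is positive above a cut-off c. If a proportion p of the weaker arm responds, c = z(1−p), and the mean difference among responders, in SD units, is

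[1 + φ(c−1)/(1−Φ(c−1))] − φ(c)/p.

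For p = 0.5, c = 0: 1.288 − 0.798 = 0.490, so about half of the true shift is lost.

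**Power.** Simulation under the same model: 8 v 8, exact rank-sum test, 10,000 trials per row, Monte Carlo SE at most 0.005.

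| Responding, weaker / better arm | Difference among responders (SD) | Power, responders only | Power, all ranked | Power, Fisher on response | p<0.05 impossible among responders |
|---|---|---|---|---|---|
| 30% / 68% | 0.36 | 3% | 34% | 23% | 61% |
| 50% / 84% | 0.49 | 12% | 41% | 15% | 12% |
| 70% / 94% | 0.64 | 22% | 44% | 4% | 0.5% |
| 90% / 99% | 0.83 | 35% | 44% | 0.1% | 0% |

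The Fisher column shows that testing the proportion alone does not replace ranking everyone.

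**A different model.** Suppose instead that response does not depend on the underlying titre (4,000 trials, log-normal titres with log-SD 1). With 95% v 50% responding and equal titres among responders, the responders-only test rejects in 4% of trials and the all-participant test in 33%. With 95% responding in both arms and a 1 SD shift, the figures are 41% and 37%, so responders-only is slightly ahead.

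**The case against.** The strongest reply is that this is a descriptive Phase I trial. Protocol 2.2.1 says it is not powered for formal comparisons between groups, and protocol 10.3 and SAP 2.2 repeat the point. A response proportion with an interval, plus titres among responders, is a coherent two-part description. In the constructed example the planned output would show 25% (7–59%) against 100% (68–100%), and a careful reader would see it. Describing titres only where a titre exists is also partly forced by the assay. The wording could conceivably restrict the description and not the test. Finally, the size rests on assumed rates. The nearest precedents in the protocol are 70% after similar DNA without electroporation (2.1.8.1) and 9/11 and 9/9 after adjuvanted intramuscular protein (MUCOVAC 2), which point to the milder rows.

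Much of this stands. No confirmatory claim is lost, the proportion is reported, and the 30% row is the low end of an assumed range. It does not remove the point. The SAP does specify a test, and a test between randomised arms should compare those arms. The natural reading restricts both summary and test; if that was not intended, the sentence still needs rewriting. Even at 70% response, power is halved. The MUCOVAC 2 rates followed three adjuvanted intramuscular doses, whereas this trial gives one intradermal protein dose after DNA priming.

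**Conclusion.** The concern holds and should be fixed. The primary titre summary and the only stated primary immunogenicity test are confined to a subset defined after randomisation, and no between-group test covers the component left out.

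Under a uniform 1 SD shift, the difference among responders shrinks to 0.36–0.83 SD and power falls from 34–44% to 3–35%, the loss being largest when few respond. These sizes depend on assumed response rates, normal log titres with equal SD, and a titre being available only for samples positive at the endpoint visit. A uniform shift produces attenuation only; a systematic reversal would need one arm to add low-titre responders. If everyone responds, the two analyses coincide. Neither safety analysis nor trial conduct is affected.

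**What to change.** Rewrite SAP 4.5.2 as follows.

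1. Apply the rank-sum test, exact or tie-corrected, to all randomised participants with a sample at the primary time point. Give samples negative at that time point a common lowest rank. Name the pairwise comparisons, since there are three arms.
2. Report the proportion responding at week 22 by arm, with Wilson interval and Fisher's exact test.
3. Keep responders-only geometric means or medians, labelled as description. If more than half of an arm is negative, report its all-participant median as below the positivity cut-off, not as an imputed number.
4. Base responder status for this analysis on the week-22 sample.
5. Correct 4 weeks to the 2-week (week 22) endpoint.

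As a secondary matter, settle the analysis set. Protocol 10.4.2.1 assigns these analyses to the per-protocol population, which in protocol 10.4.1 includes non-randomised replacements; SAP 2.3 admits randomised participants only. Both require completing the trial, so state that week-44 attendance, planned only for known responders (protocol 7.1), is not needed for the week-22 analysis set.

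The cost is SAP wording, plus a matching clarification of the protocol's per-protocol definition or a noted departure from it. All serum is already to be screened, so no new assays or samples are needed.
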